COVER PAGE

Title: Stereo Radiography of TKA Patella Mechanics 1

NCT Number: NCT02532933 2

Date: 5/31/2019

Protocol and Statistical Plan

Stereo Radiography of TKA Patella Mechanics

NCT02532933

Protocol and Statistical Plan

The purpose of this study was to determine patellar kinematics in TKA patients with medialized and medialized anatomic patellae during a seated knee extension and a weight-bearing lunge activity high-speed stereo radiography (HSSR). Flexion of the patella in the sagittal plane was reported relative to the femur and with respect to the long axis of the tibia to enable comparison to prior reports that each of these anatomic references. Based on prior computational evaluation, we hypothesized that patients with anatomic patellar implants would exhibit greater patellar flexion relative to the femur and less tibial rotation, greater knee extension strength, and improved patient-reported outcomes compared to patients with dome patellar implants.

Twenty-seven subjects with posterior-stabilized, rotating-platform total knee arthroplasty (JNU Knee, DePuy Synthes Products, Warsaw, IN) were recruited for this study after the approval of Institutional Review Board of the University of Denver and registration on www.clinicaltrials.gov (NCT02532933). All subjects signed informed consents. A power analysis (90%) using an effect size of 0.5 degrees resulted in a sample size of 16 subjects per group [10]. Subjects were required to be at least nine years post-operation and with no reported concomitant orthopaedic conditions or neurologic disorders that hindered normal movement. All subjects were patients of the surgeon co-authors, Drs. [name] and [name], and each surgeon contributed patients from both the dome and the anatomic groups. Surgeons performed TKA using a femur-first gap-balancing operative technique [12]. Patient selection criteria for dome vs. anatomic patellae was not considered, as the focus of this study was solely on differences due to study design.

Postoperatively, at the time of testing, subjects completed *Part 2 – Function* of the Knee Society (KSS) questionnaire, the Knee injury and Osteoarthritis Outcome Score (KOOS), and the Patient's implant Performance (PKIP) Questionnaire [13–16]. Because the completion of specific activities of living were required for this study, only participants scoring good or excellent (>69) on the KSS were

27 included in the study. Height, weight, and leg dominance were recorded. Maximum isometric flexor and
28 extensor strength were evaluated at 60° knee flexion and normalized to body weight. (Cybex, Medway,
29 MA).

30 Subjects performed a non-weight-bearing seated knee extension and a weight-bearing lunge
31 activity while conventional marker-based motion capture (Vicon Motion Systems, Ltd., Oxford, UK)
32 recorded whole-body motion and HSSR captured x-ray images of the knee joint in two planes (50 Hz,
33 Figure 1). Femur, tibial tray, and patellar component CAD geometries for each subject were obtained from
34 the manufacturer. The femoral and tibial tray geometries were used to track the motion of the respective
35 implants (Autoscoper, Brown University, Providence, RI) [17]. Accuracy of the HSSR is 0.2±0.1 mm in
36 translation and 0.4±0.3 degrees in rotation, comparable to those measured in other stereo radiography
37 systems [11,18,19]. Because the patellar component is radiolucent, it was not visible in the x-ray images.
38 Thus, images of four static poses of each subject's patella were recorded with the HSSR and used to derive
39 the 3D patellar bone geometry of each subject using a previously-developed statistical shape model (SSM)
40 [20]. The resection plane of the implant was assessed based on the radiographic images and the patellar
41 component model fit on the posterior surface of the SSM developed for each subject (Figure 2).

42 Sagittal plane patellar flexion was reported with respect to a medial-lateral axis on the femur (PF
43 flexion), PF tilt was reported with respect to the inferior-superior axis of the patella, and medial-lateral
44 translation was described along the medial-lateral axis of the femur. In addition, patellar sagittal plane
45 flexion was reported with respect to the long axis of the tibia (patellotibial (PT) flexion) [21] for comparison
46 to prior work that uses PT flexion as the convention. In general, higher PF flexion is associated with lower
47 PT flexion. The maximum knee flexion achieved during each activity was measured from marker-based
48 motion capture [22].

49 Unpaired, two-tailed Student's t-tests ($p<0.05$) were used to compare kinematic measurements
50 between the dome and anatomic groups, and paired, two-tailed t-tests ($p<0.05$) were used to compare
51 kinematic measurements between the knee extension and lunge activities. Pearson's correlation coefficients
52 between measurements were calculated.

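### The power analysis calls for 16 subjects per group (32 in all) but 27 were recruited, so the 90% power for 0.5 degrees is not delivered; with the SD the plan implies it is about 84–86%

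*Combined protocol and SAP*

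**What the plan says.** The document has no numbered sections, so places are given by paragraph.

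- **Second paragraph (subjects and power).** The recruited total is given as "Twenty-seven subjects with posterior-stabilized, rotating-platform total knee arthroplasty". Two sentences later the size calculation reads: "A power analysis (90%) using an effect size of 0.5 degrees resulted in a sample size of 16 subjects per group". A literature reference is attached to that sentence. The outcome to which the 0.5 degrees applies, the SD, and the dome/anatomic split are not printed.
- **Third paragraph (questionnaires).** An eligibility rule is applied to the Knee Society score (KSS) completed at the time of testing: "only participants scoring good or excellent (>69) on the KSS were" "included in the study. Height, weight, and leg dominance were recorded". The text does not say whether the 27 were counted before or after this rule. The numeral 27 printed in the middle of that sentence is a margin line number (28 and 29 follow), so it does not settle the question.
- **Final paragraph (statistical tests).** "Unpaired, two-tailed Student's t-tests ($p<0.05$) were used to compare kinematic measurements" between the dome and anatomic groups. Paired t-tests are used for knee extension against lunge.

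**The concern.** The sample size is stated per group and there are two independent groups, so the requirement is 32 subjects. The same paragraph reports 27. Both figures are in subjects, so counting knees rather than people does not explain the gap, and no passage gives a revised calculation.

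The 90% figure is the only information a reader has on how sensitive the study is. The hypotheses are directional claims about dome against anatomic implants, and the plan tests them by p-value with no confidence intervals. A non-significant difference could therefore be taken as coming from a study with a 10% chance of missing 0.5 degrees. On the plan's own calculation, 27 subjects do not give that.

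The point is limited to the unpaired group comparison. Nothing shows that the paired comparison between activities is affected.

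**Working it through.** **1. Head count (no assumptions).** Required: 2 × 16 = 32. Recruited: 27. Shortfall: 32 − 27 = 5, and 5/32 = 16%. Two groups of 16 cannot be formed from 27.

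**2. Can the 16 per group be reproduced?** Not independently, because no SD is given. Reading 0.5 as a standardised effect does not give 16: a two-sided unpaired t-test at 90% power would need 86 per group, and a paired test 44 in total. So 0.5 degrees is taken as a raw difference, and the SD is back-solved.

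**3. Implied SD.** Inputs from the document: difference 0.5 degrees, power 90%, 16 per group. The two-sided alpha of 0.05 and the unpaired t-test come from the statistical-test paragraph; the power sentence does not repeat them. With d = 0.5/SD,

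power = P(T > t₀.₉₇₅,df), where T is non-central t with df = n₁ + n₂ − 2 and non-centrality d·√(n₁n₂/(n₁+n₂)).

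- Case A, 16/16 gives exactly 90%: d = 1.185, SD = 0.5/1.185 = 0.422 degrees.
- Case B, 16 was rounded up from just above 15 (15/15 gives 90%, 16/16 gives 91.9%): d = 1.226, SD = 0.5/1.226 = 0.408 degrees.

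**4. Power with 27 subjects.** At 14/13, √(14·13/27) = 2.596 and df = 25. The non-centrality is 1.185 × 2.596 = 3.08 (A) or 1.226 × 2.596 = 3.18 (B). No split is stated, so every row below except 16/16 is illustrative.

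| Split | Case A | Case B |
|---|---|---|
| 16/16 (plan) | 90.0% | 91.9% |
| 14/13 | 84.0% | 86.4% |
| 15/12 | 83.6% | 86.1% |
| 16/11 | 82.8% | 85.3% |
| 18/9 | 79.6% | 82.3% |

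Type II error at 14/13 is therefore about 14–16% instead of 10%.

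**5. Other ways the 16 could have been derived.** With the normal approximation, d = (1.960 + 1.282)·√(2/n) = 1.146 for n = 16 and 1.184 for n = 15, so the SD is 0.422–0.436. The t-test power at 14/13 is then 81.6–84.0%. With one-sided alpha 0.05 for both the sizing and the test, it is about 85–87%. All of these are below 90%.

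**6. Could some SD give 90% with 27?** Power of 90% at 14/13 needs d = 1.299, so SD ≤ 0.5/1.299 = 0.385 degrees. At that SD the same calculation would have asked for 14 per group, not 16. The printed 16 and the printed 90% together rule it out.

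**7. Effect on precision at 14/13.** The difference detectable with 90% power is 1.299 × SD = 0.548 (A) or 0.530 (B) degrees, instead of 0.50. The 95% CI half-width, t₀.₉₇₅·SD·√(1/n₁ + 1/n₂), is 0.335 (A) or 0.323 (B) degrees, against 0.305 or 0.294 at 16/16.

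**8. Sensitivity to the SD (a separate matter from the shortfall).** If the true SD were 0.5 degrees, power would be 70% at 14/13 and 78% at 16/16. If it were 1.0, power would be 24% and 28%. Most of that drop comes from the SD, not from the five missing subjects.

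**The case against.** The strongest reply is that the power sentence is a planning statement. It says the calculation "resulted in a sample size of 16 subjects per group"; it does not claim that 27 subjects achieved 90%. That is a fair reading, and the correction below keeps the sentence in that role. It does not remove the problem, because the target and the recruited total stand in one paragraph with no word on the difference.

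The 84–86% also rests on inference. The SD is back-solved, the 14/13 split is assumed, and alpha is borrowed from the analysis paragraph. This stands: the percentage is conditional, and allowing for normal-approximation sizing the range is about 82–86%. The head count is not conditional. The reference cited for the calculation may hold the SD or the outcome, but it is not available here, so the accurate statement is that the document does not print them.

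The effect is also small. The detectable difference rises by 0.03–0.05 degrees in cases A and B, and the CI half-width by about 0.03, against a stated rotational accuracy of 0.4±0.3 degrees. This too stands, and it is why the point calls for a correction and does not invalidate the study.

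Finally, loss of subjects under the KSS rule is conjecture. The document reports no removals; it only leaves unclear which count the 27 is.

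**Conclusion.** The concern holds. The plan's calculation requires 32 subjects, 27 were recruited, and the document does not explain or adjust for the difference. That part needs no assumption, and confidence in it is high.

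The size of the loss depends on taking 16 per group at 90% as a correct calculation. For a near-equal split, power for 0.5 degrees is then about 84–86%, or as low as 82% under normal-approximation sizing. An uneven split lowers it further, as would removals under the KSS rule if the 27 were counted before it. No split of 27 reaches 90% with any SD consistent with the plan's figures. The loss is modest, but the stated power is wrong for the number recruited and should be corrected.

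**What to change.** Keep the existing sentence as the planned target and add text such as:

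> Of the 32 subjects planned, 27 were recruited. [n] dome and [n] anatomic subjects were analysed; [n or none] were removed under the KSS >69 rule. The calculation was for [outcome], assuming an SD of [value] degrees. With the analysed group sizes, power for 0.5 degrees under those assumptions is [x]%.

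If the SD used was 0.41–0.42 degrees, x is about 84–86 for a 14/13 split; recalculate it for the actual SD and group sizes. Report each dome–anatomic difference with its 95% confidence interval, so that a null result is judged by what the data exclude and not by the planned 90%.

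The cost is one or two sentences and the intervals, from facts the sponsor should already hold. The stated power becomes less favourable. No extra enrolment is proposed.

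### Patients are included only if they score above 69 on a KSS taken years after implantation, so the hypothesised patient-reported benefit is judged in a set selected on such an outcome

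*Combined protocol and SAP*

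**What the plan says.** All references are to the Protocol and Statistical Plan.

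- **Hypothesis (first paragraph).** Four advantages are expected of the anatomic implant: two kinematic ones, and "greater knee extension strength, and improved patient-reported outcomes compared to patients with dome patellar implants".
- **Time since surgery (second paragraph).** "Subjects were required to be at least nine years post-operation".
- **Questionnaires (third paragraph).** "Postoperatively, at the time of testing, subjects completed" the Function part of the KSS, the KOOS and the PKIP.
- **Inclusion rule (third paragraph).** "only participants scoring good or excellent (>69) on the KSS were" "included in the study. Height, weight, and leg dominance were recorded". The reason given is feasibility: "Because the completion of specific activities of living were required for this study".
- **Implant choice (second paragraph).** "Patient selection criteria for dome vs. anatomic patellae was not considered". Randomisation is not described.
- **Number (second paragraph).** "Twenty-seven subjects with posterior-stabilized, rotating-platform total knee arthroplasty" were recruited. The text does not say whether this count is before or after the KSS rule was applied.
- **Analysis (final paragraph).** The between-group t-tests are named for kinematic measurements only. No test of KSS, KOOS or PKIP is specified.

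The plan gives no count of people failing the rule, no adjustment for it, and no wording that confines the patient-reported hypothesis to well-functioning patients. It does not say outright which part of the KSS the threshold applies to. I read it as Part 2 (Function), the only part listed as completed.

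**The concern.** A threshold on a baseline characteristic narrows the population but leaves a between-group comparison interpretable within it. This threshold is on a score measured after the implant has had years to act, and that score is one of the three questionnaires available for the hypothesis. If the patellae differ in their effect on function, different kinds of patients are removed from each group, and the groups that remain are no longer comparable on patient-reported outcome.

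The feasibility reason supports the rule for the seated extension and the lunge. It gives no reason to leave low scorers out of a questionnaire comparison, since answering a questionnaire does not require performing either activity.

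What is at stake is the conclusion on one of four hypothesised items. A null could be read as showing that the two designs serve patients equally well, and a positive result as showing an implant benefit. The included set supports neither reading for recipients in general.

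**Working it through.** **Inputs.** From the documents: the threshold of 69, the 27 recruited, and the two-sided 0.05 level (stated for kinematics). The documents give no KSS mean, SD, scale range, correlation with KOOS or PKIP, or number excluded. Every other input below is assumed. The plan has no figure of its own to reproduce on this point; its 16 per group is set in degrees and does not bear on the questionnaires.

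**(a) Normal scores, equal SDs, pure shift.** The mean among those above 69 is μ + SD × φ(a)/(1 − Φ(a)), with a = (69 − μ)/SD. Take dome 75 and anatomic 85, a true difference of 10.

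- SD 15, dome: a = −0.400, mean = 75 + 15 × 0.3683/0.6554 = 83.43; 34.5% fail.
- SD 15, anatomic: a = −1.067, mean = 85 + 15 × 0.2259/0.8569 = 88.95; 14.3% fail.
- Difference left at SD 15: **5.53** (before rounding of the means).
- SD 10: 86.17 − 79.59 = **6.58**; 27.4% and 5.5% fail.

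For dome means from 70 to 85 and SDs from 10 to 20, between 4.3 and 9.0 of the 10 points remain.

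**(b) Another questionnaire with the same SD and a true difference of 10.** If its within-group correlation with KSS is r, the difference left is 10 + r × (5.53 − 10) at SD 15. This gives 8.66, 7.76 and 6.87 for r = 0.3, 0.5 and 0.7. At r = 0 nothing is lost.

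**(c) Scale bounded at 0 to 100.** Beta distributions matched to each mean and SD, with the mean above 69 found numerically:

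| Dome mean (SD) | Anatomic mean (SD) | True difference | Difference above 69 |
|---|---|---|---|
| 75 (15) | 85 (15) | 10 | 6.71 |
| 75 (10) | 85 (10) | 10 | 7.27 |
| 80 (10) | 90 (10) | 10 | 8.52 |
| 75 (10) | 80 (15) | 5 | 6.70 |
| 75 (15) | 80 (10) | 5 | −0.34 |
| 75 (10) | 75 (15) | 0 | 3.63 |

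In the third row 14.2% and 4.8% fail, and the loss is smaller. The last three rows show that, with unequal SDs, the rule can enlarge, reverse or create a difference.

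**(d) Equal SDs do not guarantee shrinkage.** Let half of dome score 64 and half 84 (mean 74, SD 10), and half of anatomic 70 and half 90 (mean 80, SD 10). The true difference is +6. Above 69, dome keeps only the 84s and anatomic keeps everyone (mean 80), so the difference becomes 80 − 84 = −4. The example is artificial; it only disproves a general rule that the bias is toward zero.

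**(e) Small sample.** Assume a 13/14 split, all 27 included, and normal scores at 75 and 85 with SD 15. Without the rule, the noncentrality is (10/15)/√(1/13 + 1/14) = 1.73 on 25 degrees of freedom, and power is 0.384. With the rule, 200,000 simulated trials from the truncated normals give 0.231. A null is the likelier result in either case.

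**The case against.** The strongest reply is that this is a kinematic study. Its purpose, sample size and named tests all concern kinematics, and no questionnaire test is specified. The KSS rule is an ordinary study inclusion rule with a legitimate reason, and a study normally reports every measure in the subjects it includes. On that reading the patient-reported hypothesis already refers to well-functioning patients, and all that is missing is a sentence on scope. This stands as a reason to rate the point below a critical one. It does not remove it: the hypothesis is stated without that limit, three questionnaires are collected, and a comparison within the included set still conditions on something the implant may have changed.

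Four narrower points also have force.

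- **Ungated scores remove only one filter.** The patients would still be those recruited, at least nine years out, without conditions hindering movement, and with implant choice not described as randomised.
- **The scores of people who failed may not exist.** The document is written in the past tense and does not say they were kept.
- **The figures show possibility, not size.** Part (e) uses an unbounded normal, assumes the 13/14 split and assumes that all 27 passed. If few people failed, the distortion may be small.
- **The effect on KOOS and PKIP depends on a correlation the documents do not give.** Some correlation is plausible, but it is an assumption.

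**Conclusion.** The concern holds. Followed exactly, the plan selects patients on one of the outcomes it hypothesises to differ, measured after the implant could have affected it, and nothing elsewhere in the document corrects for this or limits the claim. The fault lies with the patient-reported hypothesis; the kinematic t-tests are not challenged here, and no distortion of strength or kinematics has been quantified.

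Neither size nor direction can be determined for this trial. Shrinkage follows under equal-SD normal shifts, but unequal SDs or other distributional shapes can produce the opposite. The reading that the threshold applies to KSS Function is an inference. The point should be addressed, with medium confidence, because the conclusion it affects is secondary and the extent of the selection is unknown.

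**What to change.** Keep the KSS rule for the seated extension and lunge, where it has a stated reason. Then:

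1. **If questionnaires from people scoring 69 or less were kept,** compare KSS, KOOS and PKIP in everyone who completed them. State that implant choice is not described as randomised and that the other eligibility conditions still apply.
2. **If they were not kept,** either drop improved patient-reported outcomes as a tested hypothesis, or limit that conclusion to patients with KSS above 69. In the second case, say that the rule may have distorted the difference in either direction and that a null may also reflect the small sample (27 recruited).
3. **State once that the strength and kinematic results apply to patients with KSS above 69.** This is a scope note.
4. **Report by implant group how many people failed the rule,** and whether the 27 were counted before or after it was applied.

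Items 2 to 4 cost wording and a screening count. Item 1 is a re-analysis, possible only if the scores exist; no new data are needed. The drawback is that the questionnaire and kinematic analyses may use different sets of patients, or that the patient-reported conclusion becomes narrower.
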